Are investigational drugs, devices, or biologics (test articles) controlled by the Principal Investigator? (See FDA IND and IDE Guidance for information regarding test article control).	 Yes  No If "Yes", describe your plan for control of the test article:	
List any approved drugs, biologics and/or devices being studied:		
G. Other Approvals/Regulated Materials: Does this research involve the use of the regulated materials listed below? If "Yes", additional approvals may be required.		 Yes  No

 - Controlled Substances - Radiation - Human Embryonic Stem Cells – The WHHS IRB cannot approve stem cell research - Fetal Tissue – The WHHS IRB cannot approve research involving fetal tissue 		

PART 2: STUDY DESIGN

Complete items A-E using clear, concise, non-technical, lay language (i.e., the type of language used in a newspaper article for the general public) wherever possible. Define all acronyms.

Space limits are recommendations and should be adjusted as needed, but the total length for sections A-E should not exceed 5 pages.

A. Synopsis (Briefly summarize the research.)	Space limit: quarter page
--	---------------------------

Study Description: This is a randomized prospective study comparing two postoperative leg sleeves. The novel bioactive sleeve (Reparel Leg Sleeve) will be compared to a regular TED stocking. The main hypothesis for this study is that postoperative use of a novel bioactive sleeve after hip replacement will decrease pain and improve patient reported outcome scores faster and more reliably than the control standard TED stocking. In order to test this hypothesis, approximately 50 patients scheduled for hip replacement will be randomized to one of two arms (bioactive sleeve on operative leg and TED stocking on other, versus bioactive sleeve on nonoperative leg and TED stocking on operative leg). The following standard assessment tools will be assessed: patient reported outcomes (VAS, HOOS JR, VR12, and HSS, Satisfaction, Forgotten Joint), study questionnaire. PROMs will fall under chart review activities.

Objectives:

Primary Objective: Assessing the effectiveness of a bioactive sleeve against a non-bioactive TED leg sleeve with regard to pain, swelling, and dvt rates.

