Primary Endpoint: Patient reported outcome scores (VAS, HOOS JR, VR12, HSS, Satisfaction, Forgotten Joint).

Secondary Endpoints: Swelling evaluated by routine clinical evaluations. DVT rates monitored.

Study Population: This prospective study hopes to enroll approximately 50 male and female patients over the age of 18 years old and below the age of 90 years old. BMI must be below 40. Subjects volunteer for participation with elective hip replacement.

Description of Study Intervention: This is a device study using a novel bioactive sleeve which is assumed to mimic the effects of photobiomodulation in comparison to a placebo sleeve.

Study Duration: Study duration from when the study opens until the completion of data analysis is expected to be 24 months.

B. Purpose (Specify the hypotheses and/or objectives.)	Space limit: half page
---	------------------------

This prospective study will evaluate pain, swelling, dvt rates as well as narcotic use in post-operative total hip arthroplasty patients using novel non-compressive photobiomodulating stocking (NCPS) versus current standard of care gradient compression stocking (Thrombo-Emolic-Deterrent or TED hose). Disadvantages of standard TED stockings are difficulty of placement, and thereby compliance in the postoperative period. Current literature remains mixed regarding the effectiveness of these stockings in pain, swelling, and dvt reduction. This study will evaluate if NCPS is equivalent, or superior, in these outcome areas, and it may provide a new and comfortable way to reduce patient pain and swelling immediately following hip surgery.

C. Background (Summarize previous research. Explain the rationale for the proposed investigation and if applicable how this research differs from local standard of care.)

Space limit: one page

Total hip arthroplasty (THA) is one of the most common surgical procedures today. It is designed and proven to effectively reduce pain caused by end-stage osteoarthritis. Despite its achievements, post-operative swelling of the hip and leg is thought to be a contributor to pain and delayed rehabilitation.

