A potential solution to the problems posed by traditional compression stocking is the NCPG. The garment is comprised of a semi-conductive material ground to nanoparticles that are embedded into the fibers, formed into a three-dimensional woven fabric for optimized comfort. Instead of relying on compression, NCPS utilizes the body's own thermal energy to generate infrared energy. The infrared energy generated is reflected back at the body and modifies cellular activity at the level of the mitochondria through a process known as photobiomodulation. This process of photobiomodulation is hypothesized to improve swelling and tissue healing by increasing the activity of mitochondria and the availability of cellular energy in the form of ATP.

WASHINGTON HOSPITAL HEALTHCARE SYSTEM
INSTITUTIONAL REVIEW BOARD

D. Design	
1. (Check all that apply):	
[x] Phase I [] Phase II [] Phase III [] Phase IV [x] Randomized [] Blinded	
[] Behavioral [] Interventional	
[] Multicenter: If so, is Washington Hospital the coordinating center or the primary grant holder?	[] Yes [] No
2. Additional description of general study design . Attach flow diagram if appropriate. Space limit: half page	
Inclusion Criteria	
1. Age range: from 18 to 89	
2. Primary unilateral Total Hip Replacement	
Exclusion Criteria	
1. Physical condition prohibiting use of leg stocking or garment	
2. Allergy to silicone/polyester	
4. Current DVT	
5. History of Vascular Bypass Surgery on Operative Limb ie) Fem-Pop or Fem-Fem	
6. Inability to follow standardized post op and rehab protocols	
7. Lymphedema	
Number of Research Participants	
We will enroll 50 subjects throughout all sites involved in the study.	
E. Data Analysis (How and by whom will data be analyzed?) Space limit: half page	
PI and reparel sponsor will analyze subject questionnaires using statistical data analysis using the results provided by each subject and the PI. Study team will evaluate each criterion and analyze the results of each subject. Routine clinical evaluations will be summarized. The information will be statistically summarized using the criteria identified above and measuring based upon the subject's questionnaires	

WASHINGTON HOSPITAL HEALTHCARE SYSTEM
INSTITUTIONAL REVIEW BOARD

PART 3: PROCEDURES

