
A. List, in sequence, all research procedures, tests and treatments required for the research. Indicate which would be done even if a subject does not enroll in the research. Include a detailed explanation of any experimental procedures. Attach table if available.
 
1. PI will identify 50 subject candidates willing to participate in the study. 2. Subjects randomized to bioactive sleeve on one leg and TED stocking on other. 3. Routine clinical evaluations performed 4. Patient questionnaires completed 5. Questionnaires and data analyzed, summarized and results presented
	

B. List the specific locations where research procedures will be performed. Indicate how much time will be required of the subjects, per visit and in total for the research.
 
1. PI offices: [name] Orthopedics 2. Normal routine clinical followup, up to 5 minutes for questionnaires
	

C. Will any interviews, questionnaires, surveys or focus groups be conducted for the research? If "Yes," please list any standard instruments used for this research and attach any non-standard instruments. Note: All non-standard instruments must be approved by the WHHS IRB prior to use.
 
Interviews, questionnaires, surveys will be conducted for the research using oral and online communication. Standard instruments: Hoos Jr, Pain Score, Patient Questionnaire, Global 7, Forgotten Joint Score Attached forms: Reparel Patient Questionnaire
	 Yes  No

D. Will subjects or their health care provider be given the results of any experimental tests that are performed for the research? If "Yes" please describe the tests, provide a rationale for providing subjects with the experimental test results and explain what, how and by whom, subjects and their health care provider will be told about the meaning, reliability, and applicability of the test results for health care decisions.
	 Yes  No

WASHINGTON HOSPITAL HEALTHCARE SYSTEM
INSTITUTIONAL REVIEW BOARD

PART 4: ALTERNATIVES

A. Describe the alternatives to research participation that are available to prospective subjects.	
No participation nor research	
B. Is study drug or treatment available off-study? If "Yes", discuss this in the consent form.	 Yes  No  N/A

PART 5: RISKS AND BENEFITS

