A. Risks and Discomforts 1. Describe the risks and discomforts of any investigational or approved drugs, devices and procedures being used or assigned for research purposes. Describe the expected frequency of particular side effects. If subjects are restricted from receiving standard therapies during the research, also describe the risks of those restrictions.
No expected discomforts from using bioactive sleeve garment compared to traditional TED stocking. Study to assess amount of leg swelling, discomfort, dvt rate versus traditional stockings. TED stocking will be used on either operative or non-operative leg in all cases. Literature suggests this alone has an anti-dvt effect. Therefore, expected risks rare and minimal.
2. Describe the steps taken to minimize the risks/discomforts to subjects (e.g., supportive interventions or special monitoring):
Patients have clinic support and staff availability as standard of care
B. Data and Safety Monitoring Plan (DSMP): All interventional studies involving more than minimal risk must include a DSMP. A DSMP is a plan established to assure that each research study has a system appropriate oversight and monitoring of the conduct of the research to ensure the safety of participants and the validity and integrity of the data. Note: Most, but not all studies (i.e., non-interventional studies) undergoing WHHS IRB review will require a DSMP.

WASHINGTON HOSPITAL HEALTHCARE SYSTEM
INSTITUTIONAL REVIEW BOARD

This is an interventional study and thus does require a DSMP [] Yes
Describe the DSMP Plan: Patients will be evaluated with routine postoperative phone calls at intervals within 1 week, 2 week, 4 weeks. In addition, clinical evaluations will occur at 2 week, 6 week, 12 weeks. Safety will be evaluated at each of the above mentioned followups. PI will assess all data and clinical evaluations. Monthly and quarterly review of research conduct will be reviewed by PI to assure safety of study, and validity/integrity of data.
This is a non-interventional study and thus does not require a DSMP. [] Yes

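### The bypass exclusion covers the operative limb only, although one arm puts the compression stocking on the other leg

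*Protocol*

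**What the plan says.** Both exclusion lists in the protocol (Part 2.D and Part 6.C) carry the same item 5: "History of Vascular Bypass Surgery on Operative Limb ie) Fem-Pop or Fem-Fem".

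The Synopsis (Part 2.A) defines the two arms as "bioactive sleeve on operative leg and TED stocking on other, versus bioactive sleeve on nonoperative leg and TED stocking on operative leg". Part 3.A, step 2, repeats this: "Subjects randomized to bioactive sleeve on one leg and TED stocking on other". Part 5.A confirms it: "TED stocking will be used on either operative or non-operative leg in all cases". Part 2.B describes the TED as the "current standard of care gradient compression stocking (Thrombo-Emolic-Deterrent or TED hose" and the study sleeve as non-compressive.

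Other provisions bear on the same patient:

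- Item 1 of both lists excludes a "Physical condition prohibiting use of leg stocking or garment", with no limb restriction.
- Part 6.C lets the investigator exclude anyone judged to be at high risk.
- Part 7.B has the investigator select suitable subjects from the practice's own pool.
- Part 6.D has the team screen for eligibility and says that the garments are supplied at surgery.

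**The concern.** Eligibility is settled before the arm is known, so a criterion about which legs may safely be compressed has to fit both arms. Item 5 fits one. In the arm with TED on the operative leg, it screens the compressed leg. In the other arm, it screens the leg that wears the non-compressive sleeve and does not address the leg that wears TED.

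The gap concerns an isolated fem-pop bypass in the non-operative leg. A fem-fem graft joins both limbs, so item 5 would reach it.

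If item 5 is there for garment safety, a patient of this kind could be given compression on a bypassed leg without breaching the one rule that names bypass. Only the more general checks would prevent it. What is at stake is the safety of a rare participant. Bias, power and error rates are not affected.

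**Working it through.** The protocol gives no figure on this point, so there is none to reproduce. The check sets the criterion against the arms.

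**Step 1. Which leg wears what, and what item 5 covers** (arms from Part 2.A, garment properties from Part 2.B, item 5 from Parts 2.D and 6.C)

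| Arm | Operative leg | Non-operative leg | Is the compressed leg covered by item 5? |
|---|---|---|---|
| Sleeve on operative leg | Sleeve (non-compressive) | TED (compressive) | No |
| TED on operative leg | TED (compressive) | Sleeve (non-compressive) | Yes |

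Item 5 matches the compression assignment in one arm of two.

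**Step 2. Is the limb restriction typical of the list?** The numbered exclusions are 1, 2, 4, 5, 6 and 7, which makes six. Only item 5 is tied to a limb. Of the three named leg conditions (current DVT, vascular bypass, lymphedema), only bypass is restricted. Part 6.C adds age limits and the high-risk judgement, and neither refers to a limb. This shows that item 5 is the odd one out. It does not prove that the restriction is a slip.

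**Step 3. What else could exclude the patient?** Item 1, the high-risk judgement and investigator selection could each do so. None of them names bypass surgery. Allergy, current DVT, inability to follow the protocols, lymphedema, age and BMI do not cover it.

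**Step 4. Scale, as a conditional illustration only.** The protocol gives neither the prevalence of such a bypass nor an allocation ratio. Assume 1:1 allocation and let *k* be the number enrolled with an isolated non-operative fem-pop bypass. The expected number with TED on the bypassed leg is 0.5 × *k*.

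| *k* | Share of 50 | Expected with TED on that leg |
|---|---|---|
| 0 | 0% | 0 |
| 1 | 1/50 = 2% | 0.5 |
| 2 | 2/50 = 4% | 1 |

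**Step 5. Could follow-up stand in for the criterion?** Part 5.B plans contact as follows: "Patients will be evaluated with routine postoperative phone calls at intervals within 1 week, 2 week, 4 weeks", and "clinical evaluations will occur at 2 week, 6 week, 12 weeks. Safety will be evaluated at each of the above mentioned followups". The first call therefore comes up to 7 days after surgery and the first visit at about 14 days. Part 5.A adds that clinic support is available as standard of care, and Part 9.C tells subjects to stop using the garments and consult if they feel discomfort, so use could end sooner. All of these act after the garment is on.

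**The case against.** The strongest reply is a dilemma. Either a bypassed leg must not wear TED, in which case the patient has a condition that prohibits the stocking and item 1 excludes them whichever leg is affected, or TED is acceptable on such a leg and no harm follows. Item 1 is also a listed exclusion: once it is judged to be met, exclusion is not optional. In addition, the protocol never says that a graft contraindicates compression. Item 5 may exist only to keep operative-leg outcomes free of vascular disease, and in that case its wording is right.

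Much of this stands. The safety purpose is an inference, item 1 is a real safeguard, and the practice's records allow surgical history to be reviewed at screening. But the authors wrote a separate bypass rule alongside item 1. A screener who reads a rule expressly limited to the operative limb could reasonably conclude that a bypass in the other leg is acceptable. Item 1 works only if the screener recognises bypass as a prohibiting condition, and the wording of item 5 points the other way. If item 5 serves outcome purity alone, then no specific bypass rule protects either leg, and the general checks carry the whole burden. The same edit settles the matter on either reading.

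**Conclusion.** The concern holds, as a minor point. The only rule that names bypass surgery does not match the legs that randomisation can assign to compression. An isolated fem-pop bypass in the non-operative leg is left to item 1 and the investigator's judgement.

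The number of patients affected cannot be derived from the protocol and is probably very small, possibly zero. The illustration rests on assumed values of *k* and assumed 1:1 allocation. The practical importance rests on reading item 5 as a garment-safety rule, which the protocol does not state. Confidence is therefore medium.

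**What to change.** In both exclusion lists (Part 2.D and Part 6.C), reword item 5 as: *History of vascular bypass surgery on either lower limb (e.g. fem-pop or fem-fem)*. Check it by chart review before randomisation.

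The cost is one phrase in two places and one question added to the eligibility screening already described in Part 6.D. The downside is the possible loss of a rare candidate. Part 6.A expects to consent and screen 70 people to enrol 50, a margin of 70 − 50 = 20. One candidate lost is 1/70 = 1.4% of those screened, or 1/20 = 5% of that margin.

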2. How will the investigator maintain privacy in the research setting(s)? All data will be in the privacy of the subject's home or office clinic. Confidentiality of participants Protected Health Information (PHI) will be protected through locked cabinets for participant records containing PHI. Investigators will utilize password protected programs and access to PHI will be limited to investigators only. Data collected from questionnaires and during testing will be stored in a locked cabinet that is accessible only to study personnel. Participants will not be identifiable by name or description in publications of this study.
3. What are the consequences to participants of a loss of privacy (e.g., risks to reputation, insurability, and other social risks)?

WASHINGTON HOSPITAL HEALTHCARE SYSTEM
INSTITUTIONAL REVIEW BOARD

No additional data or information collected that is not standard. Therefore, same risks of privacy loss as with any EMR system.
		

The following questions address confidentiality issues:
		

4. Identifiers: Please indicate all identifiers that may be included in the research records for the study. Check all that apply.
		
 Names  Dates  Address  Phone numbers  Fax numbers  Email address	 Social Security numbers  Medical records numbers  Health plan numbers  Account numbers  License/Certificate numbers  Vehicle id numbers	 Device identifiers/Serial numbers  Web URLs  IP address numbers  Biometric identifiers  Facial Photos/Images  Any other unique identifier  None of the 18 identifiers listed above

5. Determining Whether HIPAA Regulations Apply to This Research: Please answer the questions below for the identifiers marked in the above section. Check all that apply:
		

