
Are research data:
 
 Derived from a medical record?  Added to the hospital or clinical medical record?  Created or collected as part of health care?  Used to make health care decisions?
	
HIPAA regulations apply.
	

 Obtained from the subject, including interviews, questionnaires?  Obtained from a foreign country or countries only?  Obtained from existing research records?
	
HIPAA regulations do not apply.
	

If HIPAA regulations apply, you are required to obtain individual subject authorization or a waiver of authorization. This authorization requires a separate signature by the research subject.
		

6. Use and Disclosure of Protected Health Information: Please indicate to whom or where you may disclose any of the identifiers listed above as part of the study process. Check all that apply:
 
 The subject's medical record.  The study sponsor: please indicate: Reparel  The US Food & Drug administration (FDA)  Others: please indicate: IRB  A Foreign County or Countries  We do not plan to share any of the PHI listed above outside the research team.
		

7. Data Security: Identifiable data should not be stored on laptops, PDA's or other portable devices. Please indicate how study data are kept secure Check all that apply:
 
 Data are coded; data key is destroyed at end of study or provide date: _____  Data are coded; data key is kept separately and securely  Data are kept in locked file cabinet  Data are kept in locked office or suite  Electronic data are protected with a password  Data are stored on a secure network
		

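### Open trial with patient-reported primary scores: the protocol allows oral collection and assigns analysis to the PI and the garment's sponsor, leaving avoidable room for bias that self-completion and arm-coded data would cheaply reduce

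*Protocol*

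**What the plan says.** - **Blinding.** The design checklist in Part 2.D reads "x] Randomized [] Blinded", with the second box empty.
- **Endpoint.** Part 2.A gives "Primary Endpoint: Patient reported outcome scores (VAS, HOOS JR, VR12, HSS, Satisfaction, Forgotten Joint". All six are reported by the patient.
- **Collection.** Part 3.C states "Interviews, questionnaires, surveys will be conducted for the research using oral and online communication". Part 2.A adds that "PROMs will fall under chart review activities". Neither place says which instrument is taken by which route, who asks the questions, or that the route is the same in both arms.
- **Analysis.** Part 2.E states "PI and reparel sponsor will analyze subject questionnaires using statistical data analysis", working from what the patients and the PI supply. Part 5.B adds that the PI assesses all data and clinical evaluations.
- **Data handling.** Part 5.D.2 says "access to PHI will be limited to investigators only". Part 5.D.4 ticks names, dates and addresses as identifiers, and Part 5.D.6 ticks the sponsor as a recipient of identifiers. In Part 5.D.7 the option "Data are coded; data key is kept separately and securely" is not ticked, nor is the other coding option.

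**The concern.** The main hypothesis in Part 2.A is directional: the sleeve is expected to reduce pain and improve scores faster than the TED stocking. Every patient wears one garment of each kind and can tell them apart, so the rater of the primary endpoint is unmasked and cannot realistically be masked. That makes it more important to control the two remaining routes by which knowledge of allocation can reach the result.

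The first route is collection. A score given aloud to someone who knows which garment is on the operated leg can be influenced by that person. The protocol permits oral collection and sets no rule that would prevent this.

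The second route is analysis. One of the two named analysts is the garment's sponsor and the other is the treating investigator. If they see the arms while deciding on exclusions, visits and which scores to emphasise, those decisions can lean towards the sleeve.

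Neither effect can be separated from a true treatment effect once the data are collected and analysed. Both can be reduced beforehand at little cost.

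**Working it through.** **What the text establishes**

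| Element | Where | Stated | Not stated |
|---|---|---|---|
| Masking | Part 2.D | Blinded box empty | Any masked interviewer, assessor or analyst |
| Primary endpoint | Part 2.A | Six patient-reported scores | – |
| Collection route | Parts 2.A, 3.C | Oral and online; also called chart review | Which instrument by which route; who asks |
| Analysts | Part 2.E | PI and sponsor | Whether they see arm labels |
| Identity coding | Part 5.D.7 | Both coding boxes empty | Anything on arm coding |
| Access to identifiers | Parts 5.D.2, 5.D.6 | Investigators only; also disclosed to the sponsor | How the two fit together |

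The first five rows together give the point: subjective outcomes, an open design, a permitted oral route and interested analysts, with no safeguard described. The sixth row is a separate inconsistency about confidentiality.

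**Illustration of size**

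The protocol gives 50 patients but no significance level, power, effect size or SD, so it has no figure of its own to reproduce. The inputs are:

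- n = 25 per arm. The total of 50 is in Part 2.D; the 1:1 ratio is assumed.
- Two-sided 5% test on one score, two-sample t-test, 25 + 25 − 2 = 48 degrees of freedom (assumed). The critical value is 2.011.
- True effect zero.
- Total reporting bias b towards the sleeve of 0.2, 0.3 or 0.4 SD (assumed; the protocol gives no basis for any value).

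The noncentrality is b × √(n/2) = b × √12.5 = 3.536 b. The chance of a significant result favouring the sleeve is P(T > 2.011), with T noncentral t on 48 degrees of freedom.

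| b (SD) | Noncentrality | Noncentral t | Normal approximation, 1 − Φ(1.96 − 3.536 b) |
|---|---|---|---|
| 0 | 0 | 2.5% | 2.5% |
| 0.2 | 0.707 | 10.3% | 10.5% |
| 0.3 | 1.061 | 17.9% | 18.4% |
| 0.4 | 1.414 | 28.3% | 29.3% |

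The two methods agree closely. The quantity b is the total bias: patient expectation plus interviewer influence plus analyst choices. The table therefore shows how sensitive a trial of this size is to bias of any origin. It does not show how much the fix would remove.

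**The case against.** The strongest reply is that much of the worry rests on silence. Four parts of it stand and limit the point.

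- **Arm coding.** A reader might infer from the empty boxes in Part 5.D.7 that the data are analysed with arms visible. Those boxes concern identity, and the protocol says nothing on arm labels. Empty boxes on this form are also weak evidence: the locked-cabinet box in Part 5.D.7 is empty although Part 5.D.2 describes a locked cabinet. Masking at analysis could be set out in a statistical analysis plan, which was not available.
- **Oral scores.** A reader might infer that staff who know the allocation will take scores verbally. Part 3.C covers interviews, questionnaires and surveys in one sentence and names no asker. Other wording in Parts 2.E, 3.A and 6.D is compatible with patients filling in the forms themselves.
- **Size.** The bias range is assumed, and part of any bias is patient expectation, which neither change touches. It would also be tempting to size the analyst's freedom by the chance of at least one nominally significant result among six scores. That chance measures multiplicity and is the same whether the arms carry names or letters, so it is not used here.
- **Masking the PI.** The PI selects patients from his own pool (Part 7.B), the garments are supplied at surgery (Part 6.D), and the PI assesses all the data. With 50 such patients, letter labels would mask the PI poorly.

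The reply does not dispose of the rest. Part 2.E itself names the analysts, Part 3.C itself permits the oral route, and online collection is already planned. The remedy therefore mostly narrows what the protocol already provides for.

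**Conclusion.** The point holds as a cheap improvement that should be made, not as proof of a biased analysis. The protocol combines an open design, six patient-reported primary scores, a permitted oral route and analysis by the PI and sponsor, and describes no safeguard on collection or analysis. It does not state that scores are taken by allocation-aware staff or that the analysts see the arms.

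The one-directional error rates of 10%, 18% and 28%, against a nominal 2.5%, depend on 1:1 allocation, a single score tested at two-sided 5%, and an assumed total bias of 0.2 to 0.4 SD. The interviewer and analyst share of that total is unknown, so the gain from the fix cannot be quantified.

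The conflict over identifiers between Parts 5.D.2 and 5.D.6 is real, but it is a confidentiality matter. Disclosing names, dates and addresses does not in itself bias the outcome.

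**What to change.** 1. **Part 3.C.** Make self-completion by the patient the default for every patient-reported score, online or on paper, by the same route in both arms and at all time points, and before contact with the PI. Allow oral administration only as an exception, logged with the reason and the person who asked. Align the chart-review sentence in Part 2.A with this.
2. **Parts 2.E and 5.D.7.** Give the sponsor's analyst only a dataset with study IDs and arms labelled A and B. Existing site staff keep the key and release it after the dataset and analysis code are locked. State openly that this masks the sponsor but the PI only in part.
3. **Parts 5.D.2 and 5.D.6.** Reconcile the two statements on access by sending the sponsor coded data only.

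The cost is protocol wording, a recoded dataset and possibly a few more missing forms than with oral collection. No extra patients or external analyst are needed, but the site must designate a key-holder: Part 2.E has the study team analysing results, so someone on the existing staff has to be kept out of the analysis until the key is released.
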